
Drug administration modifications of study drug/study regimen will be made to manage potential immune-related AEs based on severity of treatment-emergent toxicities graded per NCI CTCAE v4.03.
 
In addition to the criteria for permanent discontinuation of study drug/study regimen based on CTC grade/severity (table below), permanently discontinue study drug/study regimen for the following conditions:
 
 • Inability to reduce corticosteroid to a dose of ≤ 10 mg of prednisone per day (or equivalent) within 12 weeks after last dose of study drug/study regimen • Recurrence of a previously experienced Grade 3 treatment-related AE following resumption of dosing 
Grade 1 No dose modification
 
Grade 2 Hold study drug/study regimen dose until Grade 2 resolution to Grade ≤ 1.
 
If toxicity worsens, then treat as Grade 3 or Grade 4.
 
Study drug/study regimen can be resumed once event stabilizes to Grade ≤ 1 after completion of steroid taper.
 
Patients with endocrinopathies who may require prolonged or continued steroid replacement can be retreated with study drug/study regimen on the following conditions:
 
 1 The event stabilizes and is controlled. 2 The patient is clinically stable as per Investigator or treating physician’s clinical judgement. 3 Doses of prednisone are at ≤ 10 mg/day or equivalent. 
Grade 3 Depending on the individual toxicity, study drug/study regimen may be permanently discontinued. Please refer to guidelines below.
 
Grade 4 Permanently discontinue study drug/study regimen.
	
It is recommended that management of immune-mediated adverse events (imAEs) follows the guidelines presented in this table:
 
 – It is possible that events with an inflammatory or immune mediated mechanism could occur in nearly all organs, some of them not noted specifically in these guidelines. – Whether specific immune-mediated events (and/or laboratory indicators of such events) are noted in these guidelines or not, patients should be thoroughly evaluated to rule out any alternative etiology (e.g., disease progression, concomitant medications, and infections) to a possible immune-mediated event. In the absence of a clear alternative etiology, all such events should be managed as if they were immune related. General recommendations follow. – Symptomatic and topical therapy should be considered for low-grade (Grade 1 or 2, unless otherwise specified) events. – For persistent (>3 to 5 days) low-grade (Grade 2) or severe (Grade ≥ 3) events, promptly start prednisone 1 to 2 mg/kg/day PO or IV equivalent. – Some events with high likelihood for morbidity and/or mortality – e.g., myocarditis, or other similar events even if they are not currently noted in the guidelines – should progress rapidly to high dose IV corticosteroids (methylprednisolone at 2 to 4 mg/kg/day) even if the event is Grade 2, and if clinical suspicion is high and/or there has been clinical confirmation. Consider, as necessary, discussing with the study physician, and promptly pursue specialist consultation. – If symptoms recur or worsen during corticosteroid tapering (28 days of taper), increase the corticosteroid dose (prednisone dose [e.g., up to 2 to 4 mg/kg/day PO or IV equivalent]) until stabilization or improvement of symptoms, then resume corticosteroid tapering at a slower rate (>28 days of taper).

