
General Considerations	
Dose Modifications	Toxicity Management

Note: For Grade ≥ 3 asymptomatic amylase or lipase levels, hold study drug/study regimen, and if complete work up shows no evidence of pancreatitis, study drug/study regimen may be continued or resumed.
 
Note: Study drug/study regimen should be permanently discontinued in Grade 3 events with high likelihood for morbidity and/or mortality – e.g., myocarditis, or other similar events even if they are not currently noted in the guidelines.
 
Similarly, consider whether study drug/study regimen should be permanently discontinued in Grade 2 events with high likelihood for morbidity and/or mortality – e.g., myocarditis, or other similar events even if they are not currently noted in the guidelines – when they do not rapidly improve to Grade <1 upon treatment with systemic steroids and following full taper
 
Note: There are some exceptions to permanent discontinuation of study drug for Grade 4 events (i.e., hyperthyroidism, hypothyroidism, Type 1 diabetes mellitus).
	
 – More potent immunosuppressives such as TNF inhibitors (e.g., infliximab) (also refer to the individual sections of the imAEs for specific type of immunosuppressive) should be considered for events not responding to systemic steroids. Progression to use of more potent immunosuppressives should proceed more rapidly in events with high likelihood for morbidity and/or mortality – e.g., myocarditis, or other similar events even if they are not currently noted in the guidelines – when these events are not responding to systemic steroids. – With long-term steroid and other immunosuppressive use, consider need for Pneumocystis jirovecii pneumonia (PJP, formerly known as Pneumocystis carinii pneumonia) prophylaxis, gastrointestinal protection, and glucose monitoring. – Discontinuation of study drug/study regimen is not mandated for Grade 3/Grade 4 inflammatory reactions attributed to local tumor response (e.g., inflammatory reaction at sites of metastatic disease and lymph nodes). Continuation of study drug/study regimen in this situation should be based upon a benefit-risk analysis for that patient.

AE Adverse event; CTC Common Toxicity Criteria; CTCAE Common Terminology Criteria for Adverse Events; imAE immune-mediated adverse event; IV intravenous; NCI National Cancer Institute; PO By mouth.

Pediatric Considerations	
Dose Modifications	Toxicity Management

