
Hepatitis (elevated LFTs) Infliximab should not be used for management of immune-related hepatitis.
 
 
THIS shaded area is guidance only for management of “Hepatitis (elevated LFTs)” in HCC patients
 
 
See instructions at bottom of shaded area if transaminase rise is not isolated but (at any time) occurs in setting of either increasing bilirubin or signs of DILI/liver decompensation
	Any Grade	
General Guidance
	
For Any Grade:
 
 – Monitor and evaluate liver function test: AST, ALT, ALP, and TB. – Evaluate for alternative etiologies (e.g., viral hepatitis, disease progression, concomitant medications, worsening of liver cirrhosis [e.g., portal vein thrombosis]). – For HBV+ patients: evaluate quantitative HBV viral load, quantitative HBsAg, or HBeAg – For HCV+ patients: evaluate quantitative HCV viral load – Consider consulting hepatologist/Infectious disease specialist regarding change/implementation in/of antiviral medications for any patient with an elevated HBV viral load >2000 IU/ml – Consider consulting hepatologist/Infectious disease specialist regarding change/implementation in/of antiviral HCV medications if HCV viral load increased by ≥ 2-fold – For HCV+ with HBcAB+: Evaluate for both HBV and HCV as above
	
Grade 1 (Isolated AST or ALT >ULN and $\leq 5.0 \times$ULN, whether normal or elevated at baseline)
	
 • No dose modifications. • If ALT/AST elevations represents significant worsening based on investigator assessment, then treat as Grade 2 event. 
For all grades, see instructions at bottom of shaded area if transaminase rise is not isolated but (at any time) occurs in setting of either increasing bilirubin or signs of DILI/liver decompensation
	

Specific Immune-Mediated Reactions			
Adverse Events	Severity Grade of the Event (NCI CTCAE version 4.03)	Dose Modifications	Toxicity Management

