	
Grade 2 (Isolated AST or ALT $>5.0 \times \text{ULN}$ and $\leq 8.0 \times \text{ULN}$, if normal at baseline)
 
(Isolated AST or ALT $>2.0 \times \text{baseline}$ and $\leq 12.5 \times \text{ULN}$, if elevated $> \text{ULN}$ at baseline)
	
 • Hold study drug/study regimen dose until Grade 2 resolution to Grade ≤ 1 or baseline. • If toxicity worsens, then treat as Grade 3 or Grade 4. • If toxicity improves to Grade ≤ 1 or baseline, resume study drug/study regimen after completion of steroid taper. 	
For Grade 2:
 
 – Regular and frequent checking of LFTs (e.g., every 1 to 3 days) until elevations of these are improving or resolved. – Recommend consult hepatologist; consider abdominal ultrasound, including Doppler assessment of liver perfusion. – Consider, as necessary, discussing with study physician. – If event is persistent (>3 to 5 days) or worsens, and investigator suspects toxicity to be immune-mediated AE, recommend to start prednisone 1 to 2 mg/kg/day PO or IV equivalent. – If still no improvement within 3 to 5 days despite 1 to 2 mg/kg/day of prednisone PO or IV equivalent, consider additional workup and treatment with IV methylprednisolone 2 to 4 mg/kg/day. – If still no improvement within 3 to 5 days despite 2 to 4 mg/kg/day of IV methylprednisolone, consider additional abdominal workup (including liver biopsy) and imaging (i.e., liver ultrasound), and consider starting immunosuppressives (i.e., mycophenolate mofetil).^a Discuss with study physician if mycophenolate mofetil is not available. Infliximab should NOT be used.

Specific Immune-Mediated Reactions			
Adverse Events	Severity Grade of the Event (NCI CTCAE version 4.03)	Dose Modifications	Toxicity Management

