
Endocrinopathy (e.g., hyperthyroidism, hypothyroidism, Type 1 diabetes mellitus, hypophysitis, hypopituitarism, and adrenal insufficiency; exocrine event of amylase/lipase increased also included in this section)
	
Any Grade (depending on the type of endocrinopathy, refer to NCI CTCAE v4.03 for defining the CTC grade/severity)
	
General Guidance
	
For Any Grade:
 
 - Consider consulting an endocrinologist for endocrine events. - Consider, as necessary, discussing with study physician. - Monitor patients for signs and symptoms of endocrinopathies. Non-specific symptoms include headache, fatigue, behavior changes, changed mental status, vertigo, abdominal pain, unusual bowel habits, polydipsia, polyuria, hypotension, and weakness. - Patients should be thoroughly evaluated to rule out any alternative etiology (e.g., disease progression including brain metastases, or infections). - Depending on the suspected endocrinopathy, monitor and evaluate thyroid function tests: TSH, free T3 and free T4 and other relevant endocrine and related labs (e.g., blood glucose and ketone levels, HgA1c). - For modest asymptomatic elevations in serum amylase and lipase, corticosteroid treatment is not indicated as long as there are no other signs or symptoms of pancreatic inflammation. - If a patient experiences an AE that is thought to be possibly of autoimmune nature (e.g., thyroiditis, pancreatitis, hypophysitis, or diabetes insipidus), the investigator should send a blood sample for appropriate autoimmune antibody testing.

Specific Immune-Mediated Reactions			
Adverse Events	Severity Grade of the Event (NCI CTCAE version 4.03)	Dose Modifications	Toxicity Management
	Grade 1	No dose modifications.	
For Grade 1 (including those with asymptomatic TSH elevation):
 
 - Monitor patient with appropriate endocrine function tests. - For suspected hypophysitis/hypopituitarism, consider consultation of an endocrinologist to guide assessment of early-morning ACTH, cortisol, TSH and free T4; also consider gonadotropins, sex hormones, and prolactin levels, as well as cosyntropin stimulation test (though it may not be useful in diagnosing early secondary adrenal insufficiency). - If TSH < 0.5 × LLN, or TSH >2 × ULN, or consistently out of range in 2 subsequent measurements, include free T4 at subsequent cycles as clinically indicated and consider consultation of an endocrinologist.

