	Grade 3 or 4	
For Grade 3 or 4 endocrinopathy other than hypothyroidism and Type 1 diabetes mellitus, hold study drug/study regimen dose until endocrinopathy symptom(s) are controlled.
 
Study drug/study regimen can be resumed once event stabilizes and after completion of steroid taper.
 
Patients with endocrinopathies who may require prolonged or continued steroid replacement (e.g., adrenal insufficiency) can be retreated with study drug/study regimen on the following conditions:
 
 1 The event stabilizes and is controlled. 2 The patient is clinically stable as per investigator or treating physician's clinical judgement. 3 Doses of prednisone are ≤ 10 mg/day or equivalent. 	
For Grade 3 or 4:
 
 – Consult endocrinologist to guide evaluation of endocrine function and, as indicated by suspected endocrinopathy and as clinically indicated, consider pituitary scan. Hospitalization recommended. – For all patients with abnormal endocrine work up, except those with isolated hypothyroidism or Type 1 DM, and as guided by an endocrinologist, promptly initiate empiric IV methylprednisolone 1 to 2 mg/kg/day or equivalent, as well as relevant hormone replacement (e.g., hydrocortisone, sex hormones). – For adrenal crisis, severe dehydration, hypotension, or shock, immediately initiate IV corticosteroids with mineralocorticoid activity. – Isolated hypothyroidism may be treated with replacement therapy, without study drug/study regimen interruption, and without corticosteroids. – Isolated Type 1 diabetes mellitus may be treated with appropriate diabetic therapy, without study drug/study regimen interruption, and without corticosteroids. – Once patients on steroids are improving, gradually taper immunosuppressive steroids (as appropriate and with guidance of endocrinologist) over ≥ 28 days and consider prophylactic antibiotics, antifungals, and anti-PJP treatment (refer to current NCCN guidelines for treatment of cancer-related infections [Category 2B recommendation]).^a

Specific Immune-Mediated Reactions			
Adverse Events	Severity Grade of the Event (NCI CTCAE version 4.03)	Dose Modifications	Toxicity Management

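### Appendix F gives two incompatible dosing instructions for Grade 4 adrenal and pituitary events and, as a lesser point, overlapping Grade 1 and Grade 2 transaminase ranges for HCC subjects, with no rule on which text prevails.

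*Supplement*

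**What the plan says.** Section 8.4.5 sends sites to Appendix F for immune-mediated, infusion-related and non-immune-mediated reactions, and closes by ruling out dose reduction.

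**Grade 4 endocrine events.** The Dose Modifications column of the General Considerations table states "Grade 4 Permanently discontinue study drug/study regimen". A note in the same column adds: "There are some exceptions to permanent discontinuation of study drug for Grade 4 events (i.e., hyperthyroidism, hypothyroidism, Type 1 diabetes mellitus". The endocrinopathy rows define their scope more widely, including "hypophysitis, hypopituitarism, and adrenal insufficiency". Their Grade 3 or 4 cell reads: "For Grade 3 or 4 endocrinopathy other than hypothyroidism and Type 1 diabetes mellitus, hold study drug/study regimen dose until endocrinopathy symptom(s) are controlled". It then permits a restart after the event has settled and steroids have been tapered.

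**HCC transaminases.** The shaded hepatitis rows apply to HCC patients only. Grade 1 is an isolated AST or ALT above ULN and up to 5 x ULN, "whether normal or elevated at baseline". No dose change is required, but the investigator may judge the rise a significant worsening and treat it as Grade 2. For a subject elevated at baseline, Grade 2 runs from above 2 x baseline to 12.5 x ULN, with the instruction "Hold study drug/study regimen dose until Grade 2 resolution to Grade" 1 or below, or baseline.

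**Entry.** Inclusion criterion 8 caps AST and ALT at 2.5 x ULN. Inclusion criterion 3 admits any solid malignancy that is refractory or without standard therapy, and no criterion excludes HCC.

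**The concern.** A toxicity table works only if each event and grade leads to one action. For a Grade 4 adrenal or pituitary event, one part of Appendix F ends treatment and another suspends it with a route back. Two sites could act in opposite ways on the same event and each be following the protocol. At stake is whether a subject is exposed again, at the full dose, after a Grade 4 event. In a study with 3 to 6 evaluable subjects per cohort, one subject handled differently is between a sixth and a third of the cohort's safety experience.

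The HCC overlap is a smaller matter. The same laboratory value can be recorded and managed under two grades, so holds and grades may not be comparable between sites.

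**Working it through.** **1. Grade 4 adrenal or pituitary event.** The plan has no figure to reproduce here, so the texts are compared directly.

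| Appendix F location | Covers the event? | Action at Grade 4 |
|---|---|---|
| General Considerations, Grade 4 line | Yes (all immune-mediated events) | Permanent discontinuation |
| General Considerations, exception note | Not named; three other conditions are | No exception stated |
| Endocrinopathy, Grade 3 or 4 | Yes (hypophysitis, hypopituitarism, adrenal insufficiency) | Hold; restart allowed |

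Three details bear on whether the row silently overrides the general rule:

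- The Grade 3 line of General Considerations refers the reader on to the later guidelines. The Grade 4 line does not.
- If specific rows always prevailed, the exception note would not be needed.
- Hyperthyroidism falls under the same hold-and-restart cell as adrenal and pituitary events. It is in the note; they are not. A reader could take the omission as deliberate.

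**2. DLT status.** Section 6.6.2, item 1, makes a Grade 4 immune-mediated event a DLT if it occurs in the DLT-evaluation period. The exclusion for endocrine disorders covers Grade 3 only. Neither provision refers to the dosing action taken afterwards, so DLT status is the same under either reading.

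**3. HCC overlap.** Let b be baseline AST or ALT and x the on-study value, both in multiples of ULN, with 1 < b ≤ 2.5.

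- Grade 1: 1 < x ≤ 5.
- Grade 2 with elevated baseline: 2b < x ≤ 12.5.
- Both: 2b < x ≤ 5, which contains values when 2b < 5, that is, b < 2.5. The width is 5 − 2b.

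| b | Values meeting both rows | Width |
|---|---|---|
| 1.1 | above 2.2 to 5.0 | 2.8 |
| 1.5 | above 3.0 to 5.0 | 2.0 |
| 2.0 | above 4.0 to 5.0 | 1.0 |
| 2.4 | above 4.8 to 5.0 | 0.2 |
| 2.5 | none | 0 |

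With a normal baseline, Grade 2 starts above 5 x ULN, so there is no overlap. A scan of values from 1.01 to just under 25 x ULN gave the same ranges and no gaps between rows. Example: with baseline 1.5 x ULN, an on-study value of 4 x ULN meets both the no-modification row and the hold row.

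**The case against.** **The specific row governs.** The endocrinopathy cell names Grade 4 and gives a clear instruction. The introduction to General Considerations points to the table below for grade-based discontinuation criteria. Appendix F also uses *i.e.* loosely: in the Non-Immune-Mediated Reactions table it introduces underlying disease as the meaning of an unrelated event, while Section 8.4.5 gives an accident as another instance. The exception list may therefore be illustrative. This is a plausible reading of intent, but the appendix states no order of precedence, and the omission of conditions that share a cell with a listed one leaves the opposite reading open.

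**Other safeguards exist.** Section 7.1 lets the investigator stop treatment for a DLT or other adverse event, and Section 8 requires immediate safety concerns to be discussed with the sponsor. Both reduce the risk of unconsidered re-exposure. Neither settles which Appendix F instruction applies.

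**The HCC rows have a bridge.** The significant-worsening clause lets the investigator move a Grade 1 value to the Grade 2 action. That softens the conflict. It does not remove it, because one row leaves to judgement a hold that the other requires.

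**Local tumour inflammation.** A reader might infer a further contradiction, since General Considerations also say that discontinuation "is not mandated for Grade 3/Grade 4 inflammatory reactions attributed to local tumor response". That text names the event and the grade and supplies its own benefit-risk rule in the same table. It reads as a carve-out, and only a cross-reference in the exception note is missing.

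**Conclusion.** The Grade 4 adrenal and pituitary conflict is in the current text and should be resolved. It applies to every such immune-mediated event, whether inside or outside the DLT window. The HCC overlap is arithmetically certain for any baseline above ULN and below 2.5 x ULN, but it is secondary. It concerns isolated rises of at most 5 x ULN and assumes that an HCC subject is enrolled and that baseline is within the entry cap. The documents give neither the incidence of these events nor the number of HCC subjects; the study takes at most 12 evaluable subjects.

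Two stronger conclusions are tempting and not supported. First, a reader might infer that dose escalation turns on which row a site reads. It does not: a Grade 4 immune-mediated event counts as a DLT only within the evaluation period, and there it counts under either reading. Second, a reader might infer that the HCC overlap leads to re-dosing after severe toxicity or makes a subject non-evaluable for DLT. The overlap decides only between continuing and holding. A hold before the second dose might affect evaluability but need not: under Section 6.6.2 the window runs to 14 days after the second dose if that is later, the SRC discusses interruptions due to adverse events, and non-evaluable subjects are replaced.

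What is affected is full-dose re-exposure of individual subjects and the consistency of the safety record.

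**What to change.** In Appendix F:

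1. Reconcile the Grade 4 exception note with the endocrinopathy Grade 3 or 4 cell, so that adrenal and pituitary events carry one instruction. Either text could be changed.
2. Make the HCC Grade 1 and Grade 2 ranges mutually exclusive for subjects elevated at baseline.
3. State whether the specific row or General Considerations prevails when they differ.
4. Cross-reference the local tumour inflammation text in the exception note.

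Which dosing instruction is right is for the sponsor's safety physicians. The cost is a few edited cells and one added sentence in a protocol amendment, plus a notification to sites. No extra procedures, samples or subjects are needed.

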Appendix G Abbreviations

Abbreviation or special term	Explanation
ACTH	adrenocorticotropic hormone
ADA	antidrug antibody
AE	adverse event
AESI	adverse event of special interest
ALP	alkaline phosphatase
ALT	alanine aminotransferase
AMP	adenosine monophosphate
AST	aspartate aminotransferase
ATP	adenosine triphosphate
AUC	area under the curve
AUC _{x-y}	Area under the serum concentration-time curve from X to Y
β-hCG	beta human chorionic gonadotropin
CD	cluster of differentiation
CI	confidence interval
CL	systemic clearance
CL _{ss}	clearance at steady state
C _{max}	maximum serum concentration
C _{max, ss}	maximum serum concentration at steady state
CNS	central nervous system
CR	complete response
CRC	colorectal cancer
CrCl	calculated creatinine clearance
CRF	case report form
CSR	clinical study report
CT	computed tomography
CTCAE	Common Terminology Criteria for Adverse Events
CTLA-4	cytotoxic T lymphocyte-associated antigen 4
C _{trough}	trough serum concentration
C _{trough ss}	trough serum concentration at steady state
DC	disease control
DCR	disease control rate
DLT	dose-limiting toxicity
DNA	deoxyribonucleic acid

Abbreviation or special term	Explanation
DoR	duration of response
ECG	electrocardiogram
ECOG	Eastern Cooperative Oncology Group
eCRF	electronic Case Report Form
EDC	Electronic Data Capture
FDG-PET	fluorodeoxyglucose positron emission tomography
FFPE	formalin-fixed and paraffin-embedded
GCP	Good Clinical Practice
GCV	geometric coefficient of variation
GLP	Good Laboratory Practice
Gmean	geometric mean
GMP	Good Manufacturing Practice
HBc	hepatitis B core
HBsAg	HBV surface antigen
HBV	hepatitis B virus
hCG	human chorionic gonadotropin
HCV	hepatitis C virus
HIV	human immunodeficiency virus
HPF	high power field
IATA	International Airline Transportation Association
IB	Investigator's Brochure
ICF	Informed Consent Form
ICH	International Conference on Harmonisation
IEC	independent ethics committee
Ig	immunoglobulin
IgG1 λ	immunoglobulin G1 lambda
imAE	immune-mediated adverse event
ILD	interstitial lung disease
IRB	institutional review board
IRR	infusion-related reaction
IV	intravenous
IVRS	interactive voice response system
IWRS	interactive web response system
mAb	monoclonal antibody

Abbreviation or special term	Explanation
MDSC	myeloid-derived suppressor cell
MedDRA	Medical Dictionary for Regulatory Activities
MRI	magnetic resonance imaging
NCI	National Cancer Institute
NE	not evaluable
NOAEL	no-observed-adverse-effect level
NTL	non-target lesion
